3.3 Impact estimates

The main analysis of impacts will be performed using intent-to-treat (ITT) specifications, wherein all study participants in the originally assigned program group at baseline are included in the statistical analysis and analyzed according to their program group, regardless of whether they received interventions or not. Women who refused or withdrew consent or those who are ineligible according to study protocol are excluded from ITT analysis.

The main impacts of the interventions will be estimated for: (1) dietary diversity score, (2) consumption of IFA supplements, and (3) early breastfeeding practices; secondarily, impact will be estimated for exposure to key interventions: (4) maternal nutrition counseling, (5) counseling on IFA supplementation, (6) weight gain monitoring and counseling, (7) breastfeeding counseling. The impact on dietary diversity will be assessed among PW, and impact on all the remaining outcomes will be assessed among RDW.

Given that the main impact indicators with full sample sizes are collected at endline only, ITT linear regression models will be used to test the means of the outcome for estimates of group differences (intervention vs. control) at endline, with standard errors clustered at the health center level. In the ITT adjusted models, we will control for gestational age (for PW only), maternal characteristics, child age and sex (for RDW only), and other variables that may be different between study arms. Robustness tests will be conducted using difference-in-difference analysis where outcome variables exist at baseline.

Table 6: Dummy table for impact estimates

Indicator	Baseline		Endline		Unadjusted impact est.¹	Adjusted impact est.²
	A&T (N=)	Control (N=)	A&T (N=)	Control (N=)		
	Mean (SD)	Mean (SD)	Mean (SD)	Mean (SD)		
Dietary diversity score (number of food groups) Number of IFA tablets consumed						
	Percent	Percent	Percent	Percent		
Minimum dietary diversity (≥5 food groups) Consumed 90+ IFA tablets						

¹Controlling for clusters by health center

² Adjusted for gestational age (PW), maternal age and education, household food security and wealth, and clustering by health center
 *p<0.05, **p<0.01, ***p<0.001

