Across SNNPR and Somali regions, A&T selected seven woredas (districts) as potential intervention areas on the basis of having adequate health facility access and infrastructure. Four woredas were selected in SNNPR and three woredas in Somali region. Fewer woredas were selected in Somali as the communities are more homogenous, and those with less security issues were identified. The list of study woredas and their corresponding numbers of health centers and posts are presented in **Table 1**.

Table 1. Study woredas and total number of available health centers and health posts

No.	Region	Zone	Woreda	Population	Kebeles	Health Centers	Health Posts
1	Somali	Fafan	Gursum	37,425	15	3	18
2		Fafan	Harawa	32,034	16	2	15
3		Fafan	Keberi Beyah	165,518	29	5	34
4	SNNPR	Gurage	Sodo	175,400	54	7	39
5		Gurage	Muhor Na Aklil	119,137	29	5	30
6		Silti	Dalocha	89,807	18	4	18
7		Kembata Tembaro	Doyo Gena	78,634	18	4	19

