3.1 Allocation

A cluster is defined as the health center catchment area. Four woredas in SNNPR (with 18 health centers and 2 hospitals) and two woredas in Somali region (with 10 health centers) were selected as intervention areas (see **Figure 3**). The samples across the two regions will be pooled to estimate effects at program level. We will use stratified randomization to try to balance potential co-interventions and confounders. Where there are odd numbers of health centers within woredas, the remaining health centers will be randomized within the same region. Then, 15 clusters will be allocated to the intervention arm and 15 clusters will be allocated to the control arm by use of computer generated pseudo-random numbers.

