**ALIVE & THRIVE ETHIOPIA (A&T-ETHIOPIA)
MATERNAL NUTRITION IMPLEMENTATION RESEARCH (MNIR)**

**A Feasibility Study of Integrating a Package of Maternal Nutrition Interventions into Antenatal Care
Services in Ethiopia: A Cluster-Randomized Evaluation**

Data Analysis Plan

Prepared by:

[name], [name], [name], and [name]

International Food Policy Research Institute

Final version date: August 11, 2021

Trial registration number: ClinicalTrials.gov NCT04125368

Study protocol: Impact evaluation study protocol, version 2, dated June 2, 2021

Acknowledgements: This data analysis plan was prepared before commencing any analysis with the impact evaluation endline survey data. All final decisions on the statistical analyses remain with the evaluation team.

I. Study Background and Approach

In Ethiopia, Alive & Thrive (A&T) has developed and integrated a package of maternal nutrition interventions as part of the antenatal care (ANC) services provided by the government health system. Interventions are implemented in seven woredas (districts) in two regions – SNNP (4 woredas) and Somali (3 woredas). Key interventions include (1) maternal nutrition counseling (on diet quality and quantity), (2) iron and folic acid (IFA) supplementation (adequate supply and counseling), (3) weight gain monitoring (measurement and counseling), and (4) counseling on early initiation and exclusive breastfeeding practices. The interventions align with the 2016 WHO ANC guidelines (World Health Organization, 2016) and aims of the National Nutrition Program (NNP II).

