1.2 Impact evaluation study design

The impact evaluation of A&T's interventions used a cluster-randomized design with repeated cross-sectional surveys at baseline and endline. We applied stratified random allocation to 30 health centers within seven woredas, which were assigned to either the A&T intervention (15 health centers) or control areas (15 health centers). A small baseline survey was conducted in October-November 2019 and the endline survey was conducted in August-September 2021 in the same 30 health center catchment areas, thereby creating panel data at the health facility level (not at individual level). Program implementation faced major disruptions and was paused between April and September 2020 due to the COVID-19 pandemic and related state-level restrictions. Refresher training and support for implementation of interventions were reengaged starting October 2020, for full implementation duration of approximately 10 months.

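### The impact models leave out the woreda strata used for randomization; if woredas differ, the health-center-clustered standard error is too large and power goes unused

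*SAP*

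**What the plan says.** SAP 1.2 describes the allocation: "We applied stratified random allocation to 30 health centers within seven woredas". Protocol 3.1 adds the rule for leftovers: "Where there are odd numbers of health centers within woredas, the remaining health centers will be randomized within the same region". Allocation is 15 centers per arm.

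The impact model in SAP 3.3 is a linear regression for "group differences (intervention vs. control) at endline, with standard errors clustered at the health center level". The first footnote to Table 6 mentions only clustering by health center. The second reads "Adjusted for gestational age (PW), maternal age and education, household food security and wealth, and clustering by health center". The text also allows for "other variables that may be different between study arms". No stratum term appears in any of these, nor in the random effects, DID and ANCOVA text of Protocol 4.4, and no reason is given for leaving it out. The SAP does not say which of its two models is primary; both omit the strata.

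The documents also disagree on the strata. Protocol 3.1 has "two woredas in Somali region (with 10 health centers) were selected as intervention areas", while Protocol 2.1 says "Four woredas were selected in SNNPR and three woredas in Somali region". Section I of the SAP agrees with three.

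**The concern.** When allocation is balanced within woreda, differences between woredas largely cancel out of the arm comparison. The true sampling variation of the estimate is then smaller than under unrestricted allocation, and it is nearly the same whether or not woreda is in the model. A clustered standard error from a model without woreda does not know this. It treats all variation between centers as noise, including the part that the design removed.

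The result is confidence intervals that are too wide and tests stricter than 5%. With only 30 clusters, that can leave a real effect unconfirmed. The clause on covariates that differ between arms is unlikely to rescue the model, because a factor balanced by design tends not to look different between arms.

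There is a second risk. An analyst who notices the gap late may add woreda dummies to the specified clustered standard error, and that pushes type I error above 5%.

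**Working it through.** **Inputs.** Health centers per woreda (Protocol Table 1): Somali 3, 2, 5; SNNPR 7, 5, 4, 4; total 30. Protocol 2.6: tablets SD 30.36, ICC 0.15, 945 per arm (63 per center), difference 13; food groups SD 1.49, ICC 0.096, 270 per arm (18 per center), difference 0.61. Two-sided 5% (SAP 3.1; Protocol 4.4 says one-sided, but the stated differences reproduce only with a two-sided test).

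**The plan's own figures.** Detectable difference = SD × √(2 × DEFF / n) × (t₀.₉₇₅,₂₈ + t₀.₈₀,₂₈), with DEFF = 1 + (m − 1) × ICC.
- Tablets: DEFF = 1 + 62 × 0.15 = 10.3; SE = 30.36 × √(2 × 10.3 / 945) = 4.48; result 13.01 (stated 13).
- Food groups after baseline: DEFF = 1 + 17 × 0.096 = 2.632; SE = 0.208; result 0.604 (stated 0.61).
- Food groups at planning (SD 1.39, ICC 0.21): DEFF = 4.57; SE = 0.256; result 0.742 (stated 0.75).

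The sizing therefore takes no credit for stratification.

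**Mechanism by hand, tablets.** The variance of a center mean is 0.15 × 30.36² + 0.85 × 30.36² / 63 = 138.26 + 12.44 = 150.70, so SE = √(2 × 150.70 / 15) = 4.48. If 30% of the between-center part lies between woredas and were removed completely, 0.7 × 138.26 + 12.44 = 109.22 and SE = 3.82. Four woredas have odd counts, so removal is incomplete; simulation gives a true SD of 3.92 without woreda terms and 3.88 with them.

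**Simulation.** 40,000 runs per cell, allocation as in Protocol 3.1, equal center sizes. SAP model: least squares, Stata-type clustered SE, t on 29 df. Alternative: regression of the 30 center means on arm and woreda, t on 30 − 7 − 1 = 22 df. The woreda share of between-center variance is an assumption.

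| Woreda share | 0% | 10% | 30% | 50% |
|---|---|---|---|---|
| Tablets, SAP: type I error | 5.3% | 4.6% | 3.3% | 1.8% |
| Tablets, SAP: reported / true SE | 0.98 | 1.01 | 1.10 | 1.23 |
| Tablets, SAP: power at 13 | 81% | 82% | 84% | 88% |
| Tablets, woreda terms: power | 78% | 82% | 89% | 96% |
| Food groups, SAP: power at 0.61 | 82% | 82% | 84% | 87% |
| Food groups, woreda terms: power | 79% | 82% | 87% | 92% |

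With woreda terms and 22 df, type I error is about 5%. Woreda dummies with the default clustered SE and 29 df give 8.5 to 9.0%. Region terms alone reach 84% power for tablets at a 30% share, against 89% with woreda terms.

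**What the documents say about region.** Protocol 2.1 gives 2016 whole-region figures, which bound only the region part of the share. With 10 and 20 of the 30 centers, share = (1/3)(2/3)(pS − pN)² / [p(1 − p) × ICC], where p = pS/3 + 2pN/3 and ICC 0.15 is assumed.
- Any IFA, all women (28 v 41%): (2/9) × 0.0169 / (0.2322 × 0.15) = 11%.
- Any IFA among attenders, if all takers attended (28/44 = 64% v 41/69.6 = 59%): 1%.
- Nutrition counseling among attenders (48 v 62.3%): 12%; 19 to 9% for ICC 0.096 to 0.21.
- Four or more ANC visits among attenders (11.8/44 = 26.8% v 38.2/69.6 = 54.9%): 47%; 74 to 34% over the same ICC range.

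Region alone thus makes almost no difference for IFA (SAP type I error 4.3 to 5.3%). For ANC visits, a secondary outcome, it would overstate the SE by about 31% (type I error 1.1%).

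**The case against.** The strongest reply is that nothing planned fails. The detectable differences reproduce without credit for stratification, the SAP model keeps 81 to 88% power in every cell above, and false positives do not increase. The benefit rests on an undocumented quantity, and the only regional evidence on an IFA topic (1 to 11%) sits at or below break-even. If woredas do not differ, the change takes power to 78 to 79%, just under target. All of this stands. It makes the point one of efficiency, and any gain on the primary outcomes needs woreda differences within region. The documents suggest such differences (SNNPR, with 20 of the 30 centers, is called the most diverse region, and allocation was stratified to balance confounders) but do not measure them.

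The regional shares are also fragile. They use 2016 data for whole regions, while the trial's own baseline has 84.3% ever taking IFA. If the ICC of 0.15 is a within-region value, the ANC-visit share is 34%, and the SE is overstated by about 20% (type I error 1.8%). That stands too.

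Wealth and food security in the adjusted model may absorb part of the woreda variance. If they take half, a share s becomes (s/2)/(1 − s/2): 30% acts like 18% and 50% like 33%, and type I error is about 3 to 4%. The unadjusted model has no such help.

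The last objection is that center means weight centers equally, whereas the SAP regression weights women equally, and recruitment may be uneven. With varying center sizes, type I error of the center-mean regression stayed near 5%. At a 30% share, power rose by about 11 points for tablets and 3 for food groups, although part of the tablet gain comes from the weighting and not from the strata. The difference in what is averaged is real and should be stated. The mixed-model option and the covariate-adjusted means were not simulated.

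**Conclusion.** The concern holds. The models do not reflect the randomization, and where woredas differ the stated standard error is too large. At an assumed 30% woreda share the overstatement for tablets is 10%, type I error is 3.3%, and about 5 points of power go unused (3 for food groups). At 50% the figures for tablets are 23%, 1.8% and 8 points. At 10% or less nothing meaningful is lost. These results rest on the Table 1 strata, equal center sizes, the protocol's SDs and ICCs, and the assumed share. The matter is worth settling in the SAP, but it does not threaten the validity of the planned test or its 80% power.

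**What to change.** 1. In SAP 3.3 and the footnotes to Table 6, include woreda terms in the unadjusted and adjusted models for both primary outcomes and for the RQ2 outcomes.
2. Name the inference method with them: regression on the 30 center means (covariate-adjusted means for the adjusted model) with residual df, or a mixed model with Kenward-Roger df. State whether centers or women are weighted equally. Rule out woreda dummies with the default clustered SE on 29 df. Region terms alone are not enough if woredas differ within region.
3. Reconcile the number of Somali woredas before coding. In Table 1 the three have 3 + 2 + 5 = 10 centers, and no two of them reach the 10 given in Protocol 3.1. Seven strata leave 22 df; six would leave 23.

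Baseline adjustment is not a substitute. Tablet counts were lost at baseline through the CAPI error. For food groups, adding the center baseline mean to the woreda model changed power by −2 to +1 points at cluster autocorrelations of 0 to 0.5 (+1 to +6 at 0.8). It can serve as a sensitivity analysis.

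The cost is SAP wording and a different inference method; no new data are needed. If woredas do not differ, power falls about 3 points (tablets 81 to 78%, food groups 82 to 79%). Break-even is a woreda share of about 10% for tablets and 10 to 20% for food groups. The choice should be fixed before the endline data are analyzed.

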3.4 Plausibility analysis

In addition to the estimation of impacts, we will conduct plausibility analyses by two methods, to provide further evidence for the likelihood or strength of our impact estimates. First, we will assess whether social desirability bias may have influenced reported outcomes. Second, we will examine the intermediate outcome indicators along the program impact pathways (from service delivery to exposure and behavioral determinants) to determine whether the program resulted to the outcomes as intended by design.

3.4.1 Testing for social desirability bias

For outcome measures based on individual report, social desirability bias may play a potential role in influencing response. We applied a 13-item social desirability index, adapted from Reynolds and Gerbasi (Reynolds, 1982), to determine the extent to which respondents were likely to report behaviors based on their desire to please others, present oneself to others in a favorable way, or for social approval, i.e., “social desirability”:

No.	Question item	
1	Is it sometimes hard for you to go on with your work if you are not encouraged?	NO=1
2	Do you sometimes feel resentful when you don't get your way?	NO=1
3	Do you occasionally give up doing something because you don't think you have the ability?	NO=1
4	Do you occasionally feel like not listening to people event though you know they were right?	NO=1
5	No matter who you're talking to, are you always a good listener?	YES=1
6	Have there been occasions when you took advantage of someone?	NO=1
7	Are you always willing to admit it when you make a mistake?	YES=1
8	Do you sometimes try to get even, rather than forgive and forget?	NO=1
9	Are you always courteous, even to people who are disagreeable?	YES=1
10	Have you ever been irritated when people expressed ideas very different from your own?	NO=1
11	Have there been times when you were jealous of the good fortune of others?	NO=1
12	Are you sometimes irritated by people who ask favors of you?	NO=1
13	Have you ever deliberately said something that hurt someone's feelings?	NO=1
	Total score	13

The social desirability score (SDS) will be created by adding up the number of socially desirable answers, out of the total 13 question items. We will conduct three analyses using this score: (1) estimation of mean SDS by program group to compare differences in the level of social desirability bias between the intervention and control groups; (2) tabulation of key outcomes by SDS to assess whether the reported outcomes varied by SDS levels; and (3) regressions with each of the outcomes as dependent variables to test the interaction between SDS and intervention group, to determine whether or not social desirability bias differentially affected the impact of the A&T interventions on key outcomes.

3.4.2. Analysis of program impact pathways

The program impact pathway (PIP) was developed in collaboration with the A&T program team to map out the mechanisms through which the interventions were expected to achieve impact. The purpose of the PIP analysis is to lay out the theoretical causal links between program activities, outcomes, and impacts. We will examine key indicators along the components of pathways (addressed in part by RQ2

and RQ3), to interpret and support the impact evaluation results. We will compare differences between program groups for indicators along the pathway matched to the relevant outcomes (dietary diversity, IFA consumption, and breastfeeding practices), using linear regression models, accounting for geographic clustering.

Table 7: Measures for program impact pathways

Outcome	Key Indicators	Data source
Service providers' capacity-building and service provision:		
Training and supervision (RQ3)	
 - % NM/HEW received maternal nutrition training - % NM/HEW by training content - % NM/HEW received ANC supervision - % NM/HEW by supervision content 	N-M survey HEW survey
Service providers' knowledge (RQ3)	
 - Knowledge scores for dietary diversity, adequate intake, IFA, and weight gain monitoring - Knowledge scores for breastfeeding 	N-M survey HEW survey
Service provision (RQ3)	
 - % NM/HEW provided maternal nutrition interventions - % NM/HEW by counseling messages provided (on dietary diversity, IFA, weight gain monitoring, and breastfeeding) - % NM/HEW used job aids for maternal nutrition counseling - % HEW provided home visits to PW/number of visits in last 3 months - % HEW conducted PW conference/number of meetings in last 3 months 	N-M survey HEW survey
Beneficiaries' exposure and behavioral determinants:		
ANC visits and contacts (RQ2)	
 - # of ANC visits (at health facility) - % RDW with at least 4 ANC visits - % RDW received ANC visit in first trimester of pregnancy - # of contacts outside of health facility (home visits and GASPA's) 	PW survey RDW survey
Counseling on dietary diversity and adequate intake (RQ2)	
During ANC visits and other ANC contacts:
 
 - % RDW received counseling on maternal nutrition - % RDW received counseling on dietary diversity - % RDW received counseling on consuming adequate quantity of food 	PW survey RDW survey
Counseling on IFA supplementation (RQ2)	
During ANC visits and other ANC contacts:
 
 - % RDW received counseling on importance of IFA - % RDW received counseling on how/reminders to take IFA - % RDW received counseling on managing IFA side effects 	PW survey RDW survey
Weight gain monitoring and counseling (RQ2)	
During ANC visits and other ANC contacts:
 
 - # times weighed - % RDW weighted at least 4+ times/ at each ANC visit - % RDW received counseling about weight gain during pregnancy 	PW survey RDW survey
Counseling on early breastfeeding practices (RQ2)	
During ANC visits and other ANC contacts:
 
 - % RDW received counseling on breastfeeding practices - % RDW received counseling on early initiation of breastfeeding - % RDW received counseling on not feeding pre-lacteals - % RDW received counseling on exclusive breastfeeding 	PW survey RDW survey
Beneficiaries' knowledge and perceptions	
 - Knowledge scores for dietary diversity, adequate intake, IFA, and weight gain monitoring - Knowledge scores for breastfeeding - Beliefs, self-efficacy, and social norms score 	PW survey RDW survey

Table 8: Dummy table for program impact pathways analysis

Indicator	Baseline		Endline	
	A&T (N=)	Control	A&T	Control
	Mean (SD)			
(see indicators in Table 7)				
	Percent			

*p<0.05, **p<0.01, ***p<0.001

IV. References

- Campbell, M. K., Piaggio, G., Elbourne, D. R., & Altman, D. G. (2012). Consort 2010 statement: Extension to cluster randomised trials. *BMJ (Online)*, *345*(7881), 1–21. <https://doi.org/10.1136/bmj.e5661>
- Eldridge, S. M., Chan, C. L., Campbell, M. J., Bond, C. M., Hopewell, S., Thabane, L., Lancaster, G. A., Altman, D., Bretz, F., Campbell, M., Cobo, E., Craig, P., Davidson, P., Groves, T., Gumedze, F., Hewison, J., Hirst, A., Hoddinott, P., Lamb, S. E., ... Tugwell, P. (2016). CONSORT 2010 statement: Extension to randomised pilot and feasibility trials. *The BMJ*, *355*. <https://doi.org/10.1136/bmj.i5239>
- Hayes, R. J., & Moulton, L. H. (2017). Cluster randomised trials, second edition. In *Cluster Randomised Trials, Second Edition*. <https://doi.org/10.4324/9781315370286>

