For the sample size for recently delivered women, we used the number of IFA tablets consumed from the DHS 2016 data for SNNPR (mean: 33.19, SD: 30.36), assuming an ICC of 0.15. We calculated that a sample of 945 recently delivered women per group will be able to detect a difference of 13 tablets consumed. For the proportion of women who consumed 90+ IFA tablets, we calculated that a sample of 450 recently delivered women will be able to detect a minimum of 15% increase in women consuming 90+ IFA tablets. At baseline, an error in the final Computer-Assisted Personal Interviews (CAPI) form for recently delivered women led to missing data values for the outcome variable on total IFA tablets consumed. We instead used the percentage of recently delivered women at baseline who ever consumed IFA tablets (84.3 %) and assumed an ICC of 0.150. We estimate that the sample size will detect a 12.3% increase in women who ever consumed IFA tablets. If husbands of recently delivered women are present at the time of the endline survey, they will also be interviewed briefly about their exposure to interventions, health and nutrition knowledge and any support provided during pregnancy.

Nurse-midwives and HEWs providing ANC in the study areas will also be included in both baseline and endline surveys. Three kebeles/health posts (where HEWs fall under the supervision of corresponding health centers) will be sampled per health center catchment area. Government guidelines advise that pregnant women should receive their first and last ANC visits at the health center, and other ANC visits may be provided at health posts. Direct observations of ANC visits (two per health center and one per health post) to assess service quality, followed by exit interviews to assess client satisfaction, will be conducted at endline among a subgroup of pregnant women attending ANC at the time of the survey.

At baseline, a light data collection at all facility levels (health centers and health posts) and subsamples of pregnant and recently delivered women will be conducted to assess comparability between study arms. At endline, the full samples of pregnant and recently delivered women will be surveyed.

Thus, the overall study samples sizes are presented in **Table 3**.

Table 3. Sample sizes

	Baseline 2019		Endline 2020	
	Intervention	Control	Intervention	Control
Pregnant women	90	90	270	270
Recently delivered women/Husbands	180	180	945	945
Nurse-midwives (1 per health center)	15	15	15	15

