HEW (1 per health post)	45	45	45	45
Facility assessments (1 per health center/post)	60	60	60	60
ANC observation and exit interview (2 per health center, 1 per health post)	0	0	75	75
Total (excluding facility assessment)	330	330	1,350	1,350

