4.1.3 Nurse-midwife questionnaire

Interviews with nurse-midwives who provide ANC services at health centers will be conducted at baseline and endline and will gather information on workload and time commitments, ANC service provision, knowledge of maternal nutrition and optimal breastfeeding practices, exposure to nutrition training, and supervision.

Table 7. Description of modules in the nurse-midwife questionnaire

Module	Topic	Description	Respondent
1	Identification	Location, health center	Enumerator
2	Demographic characteristics	Age, education, years of experience and other characteristics of the nurse-midwife	Nurse-midwife

3	Time commitments and workload	Workload of the nurse-midwife, including responsibilities, time commitments, number of consultations and patients, monitoring and tracking of ANC clients, and records of ANC services provided	Nurse-midwife
4	Nutrition counseling information	Topics/messages provided as part of nutrition counseling during ANC	Nurse-midwife
5	Maternal health and nutrition knowledge	General knowledge on health and nutrition, nutrition during pregnancy, anemia, and IFA supplementation	Nurse-midwife
6	Breastfeeding and child feeding knowledge	Knowledge of the importance of early initiation of breastfeeding and exclusive breastfeeding	Nurse-midwife
7	Training exposure	Exposure to and training received on maternal nutrition	Nurse-midwife
8	Supervision and contact with other health workers	Frequency and content of supervision received from superiors, and contact with other health workers	Nurse-midwife

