2.3 Research question 3 (health system factors)

For assessing factors related to strengthening service delivery, measures will be used from the health facility checklist (health centers and posts) and N-M and HEW datasets. In the context of the overall evaluation, outcomes under this RQ3 count as secondary outcomes.

Table 4: Outcome measures for RQ3

Outcome	Indicator	Data source
Equipment and materials to support maternal nutrition services	- % HC/HP with maternal nutrition counseling job aids - % HC/HP with IFA supplementation job aid - % HC/HP with breastfeeding counseling job aids - % HC/HP with functional weighing scale - % HC/HP with currently stocked with IFA tablets - % HC/HP with register to monitor IFA stocks - % HC/HP reporting stock-out of IFA in past 6 months	Health facility checklist

Service providers' training and supportive supervision	
 - % NM/HEW received maternal nutrition training - % NM/HEW by training content - % NM/HEW received ANC supervision - % NM/HEW by supervision content 	N-M survey HEW survey
Service providers' knowledge	
 - Knowledge scores for dietary diversity, adequate intake, IFA, and weight gain monitoring - Knowledge scores for breastfeeding 	N-M survey HEW survey
Service providers' work tasks and workload perceptions	
 - % NM/HEW record-keeping on ANC services - % NM/HEW by content of record-keeping - % NM/HEW with increased workload in past 1y due to ANC services 	N-M survey HEW survey
Service providers' provision of services	
 - % NM/HEW provided maternal nutrition interventions - % NM/HEW by counseling messages provided (on dietary diversity, IFA, weight gain monitoring, and breastfeeding) - % NM/HEW used job aids for maternal nutrition counseling - % HEW provided home visits to PW/number of visits in last 3 months - % HEW conducted PW conference/number of meetings in last 3 months 	N-M survey HEW survey

III. Statistical Analysis Plan

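### SAP 3.4.2 does not use the facility-level baseline when comparing arms on RQ3 provider indicators, and several Table 4 indicators have no stated arm-comparison model

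*SAP*

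**What the plan says.** **Linked rounds.** SAP 1.2 states that the endline took place "in the same 30 health center catchment areas, thereby creating panel data at the health facility level (not at individual level".

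**Same size at both rounds.** Protocol Table 3 lists 15 nurse-midwives, 45 HEWs and 60 facility assessments per arm at baseline and again at endline. Protocol 4.1.3 says: "Interviews with nurse-midwives who provide ANC services at health centers will be conducted at baseline and endline". Protocol 4.1.4 says the same for HEWs. The women's samples, by contrast, are much smaller at baseline (90 against 270 pregnant women per arm; 180 against 945 recently delivered women).

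**RQ3 data.** For RQ3, SAP 2.3 says that "measures will be used from the health facility checklist (health centers and posts) and N-M and HEW datasets". Its Table 4 covers equipment and materials, training and supervision, knowledge, work tasks and workload, and service provision.

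**Model.** SAP 3.4.2 compares program groups "using linear regression models, accounting for geographic clustering". Of the RQ3 groups, Table 7 includes training and supervision, knowledge, and service provision. It leaves out equipment and materials (job-aid availability, scales, IFA stock and stock registers) and work tasks (record-keeping, workload). Table 8 shows arm columns at each round with a legend for significance stars and no effect column. Table 6, for the impact estimates, has unadjusted and adjusted effect columns.

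**Baseline adjustment elsewhere.** Protocol 4.4 undertakes to adjust for baseline differences across the variables of interest and names DID and/or ANCOVA. SAP 3.3 adds DID as a robustness check, but the outcomes named in that section are women's outcomes.

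**The concern.** SAP 3.3 justifies endline-only models by the lack of full-size baseline data for the main impact indicators. That reason does not apply to providers and facilities, whose baseline is as large as their endline. SAP 3.4.2 nevertheless says nothing about using it, and the protocol's commitment is lost on the way to the SAP.

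These comparisons rest on the trial's smallest samples, where precision is scarce and sizeable chance differences at baseline are common. SAP 3.4 uses the same indicators to judge whether the impact estimates are plausible. With arm means by round and no effect column, a reader of Table 8 may weigh significance at endline against significance at baseline, which is not a test of the program effect. For the Table 4 indicators outside Table 7, the analyst would have to choose a model after seeing the data.

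**Working it through.** **Inputs from the documents.** 15 clusters per arm (Protocol 3.1); one nurse-midwife per health center and three HEWs per catchment (Protocol 2.6, Table 3); 80% power and 5% significance (Protocol 2.6); two-sided tests (SAP 3.1; Protocol 4.4 says one-sided). The counts agree: 15×1 = 15, 15×3 = 45, 15×(1+3) = 60.

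**Check against the plan's own figures.** No power or detectable difference is stated for any RQ3 outcome. The women's figures reproduce with SD × √(2·DE/n) × (2.048 + 0.855), t on 28 df, DE = 1+(m−1)·ICC:
- Pregnant women, planning: DE = 1+17×0.21 = 4.57; 1.39×√(2×4.57/270)×2.903 = 0.74 (stated 0.75).
- Pregnant women, baseline data: DE = 1+17×0.096 = 2.63; result 0.60 (stated 0.61).
- Recently delivered women: DE = 1+62×0.15 = 10.3; result 13.0 tablets (stated 13).

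The design therefore works on a two-sided, 28-df basis, which is used below.

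**Nurse-midwives, 15 vs 15.** Unadjusted SE = √(2/15) = 0.365 SD. Noncentral t on 28 df gives 80% power at 1.06 SD. With ANCOVA, SE = 0.365 × √(1−ρ²) × √(1+1/27) on 27 df, where ρ is the baseline-endline correlation. The documents do not give ρ, so a range is assumed:

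| ρ | SE (SD) | Power at 1.06 SD | Detectable difference (SD) |
|---|---|---|---|
| unadjusted | 0.365 | 80% | 1.06 |
| 0.1 | 0.370 | 79% | 1.08 |
| 0.2 | 0.364 | 80% | 1.06 |
| 0.3 | 0.355 | 82% | 1.03 |
| 0.4 | 0.341 | 85% | 0.99 |
| 0.5 | 0.322 | 89% | 0.94 |

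Break-even is at ρ of about 0.2. Below that, the lost degree of freedom and the estimated slope cost about 1 point (1.5 points at ρ = 0).

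**ANCOVA rather than DID.** The DID variance relative to the unadjusted comparison is 2(1−ρ), so it is worse below ρ = 0.5. The nurse-midwife detectable difference under DID is 1.25 SD at ρ = 0.3, 1.06 at 0.5 and 0.82 at 0.7.

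**HEWs, three per cluster.** The variance of a cluster mean is ICC + (1−ICC)/3, with ICC assumed to be 0.1 to 0.3. If different posts or staff are surveyed and only the catchment component persists, the cluster-mean ρ cannot exceed ICC/[ICC+(1−ICC)/3]. This bound assumes that the catchment component is perfectly stable.

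| ICC | Unadjusted detectable (SD) | Maximum ρ | Power at maximum ρ | Power at half of it |
|---|---|---|---|---|
| 0.1 | 0.67 | 0.25 | 81% | 79% |
| 0.2 | 0.72 | 0.43 | 86% | 80% |
| 0.3 | 0.77 | 0.56 | 91% | 82% |

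Each row starts from 80% unadjusted.

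**Validity and imbalance.** This was simulated for 15 vs 15 facilities under no effect (40,000 replicates, stratification ignored). The unadjusted test rejects in 4.9–5.0% of trials and its estimate averages zero. In the 17% of randomizations where baseline means differ by more than 0.5 SD, it rejects in 7.5% (ρ = 0.3), 11.5% (0.5) or 17.4% (0.7), against about 5% for ANCOVA.

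**The case against.** **A reader might infer that the RQ3 comparison cannot separate chance baseline differences from program effects.** The documents do not support that. The arms are randomized with stratification, the unadjusted comparison is unbiased with correct size overall, and chance imbalance is already in its standard error. This objection stands in full: only precision, and protection once an imbalance is seen, are lost.

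**A reader might also take the data as a full panel of posts and providers.** SAP 1.2 says only that the facilities are linked. Under Protocol 2.2 the provider interviewed is whoever is available at that round, and nothing says that the same health posts are revisited. The link is therefore established for health centers only. A HEW gain of about 9 points, which would need ρ = 0.5, cannot be claimed: where only the catchment component persists, that value is out of reach at an ICC of 0.1 or 0.2.

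**The indicators most likely to persist are outside SAP 3.4.2.** Equipment, IFA stock and record-keeping are in Table 4 but not in Table 7. It would be wrong to say that 3.4.2 analyses them badly; the gap is that no model is stated for them.

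**SAP 3.4.2 is silent on adjustment and does not exclude it, and Protocol 4.4 already commits to it.** That is fair, and it makes this an omission to close. Likewise, Table 8 is a shell that does not say where its stars go, so misreading is a risk and not a stated method.

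**Most provider rows are percentages.** The SD-scale figures apply directly to scores only. For nurse-midwives, an unadjusted normal approximation gives detectable increases of about 49 points from 30% and 44 points from 50%. No adjusted figures were computed for these rows.

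**Conclusion.** The point holds as an omission in a secondary, supportive analysis. Provider and facility data exist at equal size in both rounds and are linked at least by health center, yet SAP 3.4.2 names no baseline term, Table 8 reports no effect, and part of Table 4 has no model. The comparison as written is valid.

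The size depends on ρ, which is unstated. For nurse-midwife scores the gain is about 2, 5 and 9 points of power at ρ = 0.3, 0.4 and 0.5, and nil or slightly negative below about 0.2. For HEWs it may be about 1 point (ICC 0.1) if posts or staff change. Little or no gain should be expected for items near zero at baseline, such as training, or where staff turnover is high. The primary conclusions are not affected.

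**What to change.** In SAP 3.4.2:

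- For RQ3 indicators measured in both rounds, including the Table 4 indicators not in Table 7, estimate the endline arm difference by ANCOVA and not by DID.
- Adjust for the same health center's baseline value. For health-post data, adjust for the same post's baseline value if it was revisited, and otherwise for the catchment's baseline mean. Cluster by health center.
- State whether the same health posts are revisited at endline.
- Add an adjusted difference (95% CI) column to Table 8 and base significance on that column.

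The cost is SAP wording, one table column and one degree of freedom (28 to 27). No new data are needed. For indicators with a low baseline-endline correlation, the price is about 1 point of power.
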